2.2 Rationale for Dose Selection

In the pivotal monotherapy Phase 2 study for R/R DLBCL, ADCT-402-201, loncastuximab tesirine was dosed every 3 weeks, with 150 µg/kg for first two cycles and 75 µg/kg for the subsequent cycles, which resulted in a high level of efficacy and was well tolerated. In addition, PK analyses show that this dosing regimen resulted in comparable exposure between Cycle 1 and subsequent cycles and that this dosing regimen resulted in consistent drug exposure across cycles. The dosing regimen chosen for this study is based on the regimen of loncastuximab tesirine used in the Phase 2 study. This study will utilize the same dosing regimen for Lonca-R as the ongoing Phase 3 clinical trial LOTIS-5 comparing the Lonca-R regimen (after a safety run-in) to R-GemOx in 2L transplant-ineligible patients with DLBCL. Treatment-naïve patients will present with levels of lymphocytes (within normal limits) which are believed to function as an antigen sink to loncastuximab tesirine. Administration of rituximab is known to reduce lymphocytes levels within a day ([Blasco, 2009](#)). Therefore, loncastuximab administration in Cycle 1 is given 1 day (+2 days) after rituximab administration.

3 Study Objectives and Endpoints

Table 3 Study Objectives and Endpoints

Objectives	Endpoints
Primary	
Cohort A To assess the efficacy of a response-adapted treatment of Lonca-R in unfit patients with previously untreated DLBCL or HGBCL or Grade 3b FL.	(Co-)Primary Endpoints: Cohort A CR rate, defined as proportion of patients with a BOR of CR according to the 2014 Lugano Classification criteria (Appendix 12.2). Cohort B 
• CR rate, defined as proportion of patients with a BOR of CR according to the 2014 Lugano Classification criteria.• Tolerability as defined by the percentage of patients completing a total of 4 cycles of therapy divided by the total number of patients.
Secondary	
Cohort A and Cohort B: 
• Further evaluate the efficacy of Lonca-R• To characterize the safety profile of Lonca-R• To characterize the PK profile of Lonca when given in combination with rituximab• To evaluate the immunogenicity of Lonca when given in combination with rituximab• To evaluate the impact of Lonca-R treatment on treatment-related and disease-related symptoms, patient-reported functions, and overall health status	Cohort A and Cohort B: 
• ORR according to the 2014 Lugano Classification, defined as the proportion of patients with a BOR of CR or PR.• 2-year PFS, defined as the proportion of patients that are PFS event-free at 2 years.• 3-yr OS, defined as the proportion of patients that are OS event-free at 3 years.• DoR defined as the time from the first documentation of tumor response (CR or PR) to disease progression or death• Frequency and severity of AEs and SAEs.

Objectives	Endpoints
	
• Changes from baseline in safety laboratory variables, vital signs, physical examinations, ECOG PS• Concentrations and PK parameters of loncastuximab tesirine PBD-conjugated antibody, total antibody, and SG3199 unconjugated warhead• Frequency of confirmed positive ADA responses, their associated titers and, if applicable, neutralizing activity to loncastuximab tesirine after treatment with loncastuximab tesirine when given in combination with rituximab• Changes in patient-reported outcomes (e.g., symptoms, functions, and overall health status) from baseline as evaluated by FACT-Lym
Exploratory	
CCI	CCI

Abbreviations: ADA, anti-drug antibody; AE, adverse event; BOR, best overall response; CR, complete response; DLBCL, diffuse large B-cell lymphoma; DoR, duration of response; EoT, end of treatment; ECOG PS, Eastern Cooperative Oncology Group scale of performance status; FACT-Lym, Functional Assessment of Cancer Therapy-Lymphoma; Lonca-R, loncastuximab tesirine and rituximab; ORR, overall response rate; OS, overall survival; PBD, pyrrolobenzodiazepine; PFS, progression free survival; PK, pharmacokinetic; PR, partial response; PS, performance status; R-CHOP, combination of rituximab, cyclophosphamide, doxorubicin, vincristine, and prednisone, SAE, serious adverse event.

4 Study Design

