8. Pregnancy test will be limited to females of childbearing potential; a final pregnancy test should be performed ≥ 12 months after the last dose of study drug has been administered (remote testing may be performed).
9. For days of loncastuximab tesirine infusion, PK will be collected predose (preferably within 2 h prior to start of infusion), and at the end (within -5 to +10 min) of Lonca infusion.
10. ADA samples will be collected predose (preferably within 2 h prior to start of infusion) on C1D2, C2D1 and then every other cycle beginning with C4. Patients who test positive for ADAs may be requested to supply additional ADA samples.

CCI

12. PRO instrument should be completed prior to clinical assessment.
13. Patients in both cohorts will receive 1 additional cycle of assigned therapy (Cycle 4) if in CR and 3 additional cycles if PR (Cycles 4-6) based on PET-CT after Cycle 3. Patients in cohort B who achieve stable disease and are receiving clinical benefit may receive 3 additional cycles (Cycles 4-6).
14. Premedication for the Lonca-R regimen consists of dexamethasone 4 mg PO/IV BID $\times 3$ days beginning the day prior to loncastuximab tesirine; premedication(s) for rituximab will be given according to institution standard.

Visit Scheduling Windows:

- Treatment Period: C1D1 is the reference day, otherwise visit day ± 2 days, except of visit day 2 where the time window is +2 days.
- EoT: Patients who complete all assigned treatment cycles of treatment should have their EoT visit performed 28 (± 7) days from the last dose of study treatment, and in any case prior to the initiation of new anticancer treatment.
- Follow-up Period: visit day ± 14 days.

1 Introduction and Background

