1.3 Loncastuximab Tesirine - Clinical Results

1.3.1 Phase 1 Study, ADCT-402-101

ADCT-402-101 (NCT02669017) is a first-in-human Phase 1 dose-escalation study of loncastuximab tesirine in R/R B-NHL patients, who have failed or are intolerant to established therapies, or have no other treatment options available. The study was completed with 183 patients enrolled.

[figure not shown]
Toxicity was manageable. The most common (observed in at least 5% of patients) Grade ≥ 3 treatment-emergent adverse events (TEAEs) were gamma glutamyl transferase (GGT) increased (21.3%); neutropenia (16.9%); anemia (15.3%); neutrophil count decreased (14.8%); thrombocytopenia (12.0%); platelet count decreased (10.4%). The TEAEs in 35 (19.1%) patients led to treatment discontinuation. Dose-limiting toxicities (DLT) were reported in 4 patients (3 thrombocytopenia and 1 febrile neutropenia).

Out of 180 evaluable patients with B-NHL, 48 (26.7%) achieved CR and 34 (18.9%) achieved partial response (PR), for an ORR of 82/180 (45.6%). Out of 137 evaluable patients with DLBCL, 32 (23.4%) achieved CR and 26 (19.0%) achieved PR, for an ORR of 58/137 (42.3%). Out of 14 evaluable patients with FL, 9 (64.3%) achieved CR and 2 (14.3%) achieved PR, for an ORR of 11/14 (78.6%). Out of 15 evaluable patients with mantle cell lymphoma (MCL), 5 (33.3%) achieved CR and 2 (13.3%) achieved PR, for an ORR of 7/15 (46.7%).

[figure not shown]

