2.1 Rationale for Study Design

This is a Phase 2, multi-center adaptive design study with two parallel cohorts which will enroll in total approximately 80 unfit or frail patients with previously untreated DLBCL (respectively Cohort A and Cohort B, n = 40 patients each). The primary objective will be to determine the safety and efficacy of loncastuximab tesirine in combination with rituximab (Lonca-R) in this patient population.

An analysis for efficacy and safety in Cohorts A and B (n = 40 each) as assigned by sGA ([Merli, 2021](#)) will be conducted. The sGA is a validated objective tool to assess fitness status to predict overall survival in older patients with DLBCL.

A response-adapted approach for both cohorts will be utilized where patients in the unfit & frail cohorts who achieve a CR after 3 cycles of therapy will receive one additional cycle of therapy (4 cycles total). Patients in the unfit cohort (Cohort A) who achieve a PR after 3 cycles of therapy will receive 3 additional cycles of therapy (6 cycles total). Patients in the frail cohort (Cohort B) who achieve a PR/stable disease (SD) will receive 3 additional cycles of therapy (6 cycles total). In the patient population being evaluated, de-escalating therapy to a total of 4 cycles in patients who achieve a CR may minimize toxicity while preserving efficacy. End of

treatment CR was recently found to be highly predictive for PFS and OS in DLBCL after first-line immunochemotherapy ([Kostakoglu, 2021](#)).

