4.1 Overview

This is a Phase 2 open-label, study of Lonca-R in previously untreated unfit/frail patients with DLBCL. The study will include a Screening Period (up to 28 days), a Treatment Period (4-6 cycles [each of 3 weeks]), and a Follow-up Period (for up to 5 years after treatment discontinuation) ([Section 4.2](#)).

A response-adapted approach will be used in this study. Two parallel cohorts will enroll patients in the study. Cohort A will enroll unfit patients and Cohort B will enroll frail patients or patients with cardiac comorbidities. Cohort A will assess efficacy and Cohort B will assess the efficacy and tolerability of Lonca-R. Fitness and frailty of the patients will be assessed based on the sGA tool developed by the FIL ([Merli, 2021](#)). See [Section 7.2](#) for details about sGA.

The study will enroll approximately 80 patients (approximately 40 patients in each cohort).

Based on the results from Cohort A and/ or B a protocol amendment will be considered to further evaluate the Lonca-R combination in these patient populations.

Enrolled patients in both cohorts will receive Lonca-R for 3 cycles. Patients who achieve CR after 3 cycles of Lonca-R treatment will continue to receive one additional cycle of Lonca-R. Patients who achieve PR after 3 cycles of Lonca-R will continue to receive additional 3 cycles of Lonca-R. Additionally, for Cohort B only, patients who achieve SD and derive clinical benefit per the treating physician may also continue to receive additional 3 cycles of Lonca-R. Details of dosing regimen are described in [Section 6.3 \(Table 4\)](#), (see [Figure 2](#)).

The duration of the study participation for each patient is defined as the time from the date of signed written informed consent to the completion of the follow-up period, withdrawal of consent, loss to follow-up, or death, whichever occurs first. Each patient enrolled in both cohorts will have the same duration of study participation.

18 weeks) or unacceptable toxicity, or other discontinuation criteria (see [Section 5.5](#)), whichever occurs first. Details of the treatment regimen are described in [Table 4](#).

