5.5.1 Discontinuation from Study Treatment

A patient may be discontinued from the study treatment for any of the following reasons:

- Adverse event
- Patient decision
- Investigator decision
- Major protocol deviation
- Lost to follow-up
- Disease progression (radiographic or clinical)
- Study termination by the Sponsor

- For Cohort A, patients who did not achieve a CR or PR after 3 cycles
- For Cohort B, patients who do not achieve a CR or PR or SD after 3 cycles
- Other

A patient with any of the following reasons will be immediately discontinued from study treatment:

- Pregnancy
- Death

IMPORTANT: Study treatment discontinuation is not equivalent to discontinuation from the study. Patients discontinuing the study treatment will be asked to perform an EoT visit ([Section 4.2.3](#)) and continue with the Follow-up period ([Section 4.2.4](#)) as per protocol.

The investigational site should make every effort to complete follow-up per protocol. If patients are unable to return to the site, patient status, including but not limited to survival status, may be obtained by site staff via phone, email, or mail.

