3.1 Overview

This is a Phase 2, multicenter, multi-cohort, open-label study of Lonca-R in unfit/frail patients with previously untreated DLBCL. Fitness and frailty of the patients will be assessed using the sGA tool developed by the FIL. A response-adapted approach will be used in this study. Two parallel cohorts will enroll patients; Cohort A will enroll unfit patients and Cohort B will enroll frail patients or patients with cardiac comorbidities (Figure 1).

A treatment cycle in the study is defined as 3 weeks (i.e., 21 days). Cohort A will assess efficacy and Cohort B will assess the efficacy and tolerability of Lonca-R. After completion of 3 cycles of Lonca-R treatment, patients who achieve CR or PR will continue to receive 1 additional cycle or 3 cycles of Lonca-R, respectively. Patients in Cohort A who do not achieve a CR or PR will discontinue study treatment. For Cohort B only, patients who achieve stable disease (SD) and derive clinical benefit per the treating physician may continue to receive additional 3 cycles of Lonca-R.

Eligible patients will be administered through IV with loncastuximab tesirine 150mcg/kg for the first 2 cycles starting at C1D2. For subsequent cycles, the dose level will be reduced to 75mg/kg. Rituximab will be dosed through IV with dose level of 375 mg/m² starting at C1D1.

Abbreviations: CR, complete response; Lonca-R, loncastuximab tesirine in combination with rituximab; PET-CT, positron emission tomography-computed tomography; PR, partial response; SD, stable disease; sGA, simplified geriatric assessment.

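### Cohort B's tolerability co-primary counts completion of 4 cycles whatever the reason for stopping, and the SAP neither analyses that rate nor links its by-reason tables to it.

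*Protocol*

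**What the plan says.** **Endpoint.** Protocol Table 3 (Section 3), in line with the synopsis, gives Cohort B two co-primary endpoints: CR rate and "Tolerability as defined by the percentage of patients completing a total of 4 cycles of therapy divided by the total number of patients". Neither place qualifies the reason for stopping.

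**Reasons for stopping.** Protocol 5.5 requires a reason and a date of discontinuation for every patient. Section 5.5.1 lists adverse event and death, but also radiographic or clinical progression, "Study termination by the Sponsor" and "For Cohort B, patients who do not achieve a CR or PR or SD after 3 cycles".

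**Route to cycle 4.** Whether cycle 4 is given depends on the response after cycle 3. CR leads to one more cycle and PR to three. For Cohort B patients with SD the texts differ. Protocol 2.1 says that those "who achieve a PR/stable disease (SD) will receive 3 additional cycles of therapy". Protocol 4.1 says that "patients who achieve SD and derive clinical benefit per the treating physician may also continue to receive additional 3 cycles of Lonca-R". The synopsis, footnote 13 of the Schedule of Events and SAP 3.1 agree with Section 4.1.

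**SAP.** Section 2.1 keeps tolerability as a Cohort B primary objective. Section 4.2 tabulates withdrawals from treatment by reason, 4.7.1 summarises the number of cycles dosed, 4.9.1.1 tabulates TEAEs leading to withdrawal, and 4.9.1.2 summarises deaths. The efficacy endpoints in Section 4.8 are CRR, ORR and DoR. Section 3.4 reports no modification to the protocol's statistical section.

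**The concern.** A rate called tolerability should tell the reader how many frail or cardiac patients could not continue because of harm. This one cannot do so alone. Because cycle 4 follows a response assessment, the rate is partly a measure of efficacy and overlaps with the other co-primary, CR rate. Sponsor termination adds a third component unrelated to either, and it is a possible reason here because the study was discontinued on 20 July 2023 (SAP 1).

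The error can run either way. Progression or closure before the end of cycle 4 makes the regimen look less tolerable than it was. A patient planned for 6 cycles who completes the fourth and then stops for toxicity makes it look more tolerable.

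The SAP does not repair this. It has no output for the 4-cycle rate and no cross-tabulation of that endpoint against reason for stopping. Followed as written, it leaves a stated primary objective without its defined estimate.

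**Working it through.** **1. Planned outputs against the endpoint.**

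| SAP section | What it gives | What is missing for this endpoint |
|---|---|---|
| 4.2 | Withdrawals by reason, patient listing | Not stated to be by cohort; no cut at cycle 4; no interval |
| 4.7.1 | Total cycles dosed, exposure listing | No 4-cycle completion rate |
| 4.8 | CRR, ORR, DoR | Tolerability not listed |
| 4.9.1.1 | TEAEs leading to withdrawal | Not stated to be by cohort; no cut at cycle 4 |
| 4.9.1.2 | Deaths and reasons | Not stated to be by cohort; no cut at cycle 4 |

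SAP 1 says that some protocol analyses are not covered. SAP 2.2 names PFS, OS and PRO as examples of what is dropped, all of them secondary. Tolerability is not named.

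**2. Method check on the plan's own figures.** The exact (Clopper-Pearson) 95% limits for x of n are the 2.5% quantile of Beta(x, n − x + 1) and the 97.5% quantile of Beta(x + 1, n − x). For n = 40 and x = 12, 16, 20, 24 this gives 16.6 to 46.5, 24.9 to 56.7, 33.8 to 66.2 and 43.3 to 75.1, matching Protocol Table 7 and SAP 3.2. The documents state no figure, target or threshold for tolerability.

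**3. Illustration.** Let a be the patients who stop before completing cycle 4 for an adverse event or death, and o those who stop early for any other reason. Completion = (n − a − o)/n, so only the sum a + o matters. I take n = 40, the planned cohort size.

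The one discontinuation figure shown is from the Phase 1 monotherapy study (Protocol 1.3.1): "The TEAEs in 35 (19.1%) patients led to treatment discontinuation". With 183 enrolled, 35/183 = 19.1% (95% CI 13.7 to 25.6). It comes from relapsed or refractory patients in dose escalation and is not limited to the first 4 cycles, so it only suggests a round value. I use a = 8, that is 8/40 = 20.0% (9.1 to 35.6).

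*Adverse-event or death stops fixed at 8/40:*

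| Other early stops | Completion | 95% CI |
|---|---|---|
| 0 | 32/40 = 80.0% | 64.4 to 90.9 |
| 4 | 28/40 = 70.0% | 53.5 to 83.4 |
| 8 | 24/40 = 60.0% | 43.3 to 75.1 |

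*Completion fixed at 28/40 = 70.0%, so 12 early stops:*

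| Adverse-event or death stops | Other early stops | Adverse-event or death rate | 95% CI |
|---|---|---|---|
| 4 | 8 | 10.0% | 2.8 to 23.7 |
| 8 | 4 | 20.0% | 9.1 to 35.6 |
| 12 | 0 | 30.0% | 16.6 to 46.5 |

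**4. Precision at the size reached.** SAP 3.2 reports 41 treated patients in total and does not give Cohort B's share. Over an assumed range of 10 to 30, a 20% adverse-event or death rate has intervals of 2.5 to 55.6 (2/10), 5.7 to 43.7 (4/20) and 7.7 to 38.6 (6/30).

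**The case against.** The strongest reply is that the plan already separates the reasons. This is largely right, and it limits the point. A reader might infer that adverse-event stops cannot be told apart from progression or sponsor closure. The documents do not support that: SAP 4.2 tabulates withdrawals for each reason, Protocol 5.5.1 lists those reasons separately, and adverse-event withdrawals and deaths have their own summaries. Toxicity stops after cycle 4 also appear there. With the listings, a reader could rebuild most of the split by hand. What is absent is the link to cycle 4 and to Cohort B, and an interval.

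Second, all-cause completion is an openly stated definition. It treats every early stop as a failure, avoids subjective attribution, and uses the shortest planned course (4 cycles) as a common cut. That is a good reason to keep the rate. It does not make the rate a measure of toxicity.

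Third, no threshold depends on the endpoint, so no decision rule is shown to fail. This stands, and it holds the matter to one of reporting.

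Fourth, SAP 1 warns that not every protocol analysis is covered. That may explain the missing rate, but the SAP keeps the objective, does not name this endpoint among those dropped, and reports no modifications. Nor does the text show that tolerability was dropped on purpose.

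Fifth, the numerical splits are assumed. That is so; they show what the definition allows, not what happened.

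**Conclusion.** The concern holds in this form: the endpoint mixes toxicity with efficacy and with study closure, the SAP plans no estimate of it, and its by-reason tables are not tied to it. It should be put right, at modest cost.

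The size cannot be computed. In the illustration the same 20.0% adverse-event or death rate goes with completion between 60.0% and 80.0%, and the same 70.0% completion goes with adverse-event or death rates between 10.0% and 30.0%. These figures assume 40 patients and invented splits.

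One further inference should be resisted: that the sponsor's decision lowered Cohort B's completion rate. The SAP gives a decision date, but not how many Cohort B patients were then short of cycle 4, nor whether their treatment was cut off. The direction of the net error is also unknown, since the definition can err both ways. The opening of Protocol 4.2.2 is missing from the text available, so I do not claim that the routes to cycle 4 set out above are complete.

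**What to change.** 1. Add to the SAP the Cohort B 4-cycle rate in the All-Treated Population with an exact 95% CI. Label it treatment completion, and state what counts as a completed cycle (for example, how a cycle with only one of the two drugs given, or an unfinished infusion, is counted).
2. In the same table, split the patients who did not complete cycle 4 by recorded reason: adverse event or death without progression; progression or lack of response; other, including sponsor termination. Give an exact 95% CI for the first proportion, and a sensitivity analysis that moves patient and investigator decisions into it.
3. Among patients who completed cycle 4 and were planned for 6 cycles, report adverse-event or death stops at any later time, including before cycle 5 starts.
4. Label the split post hoc.
5. Separately, reconcile Protocol 2.1 with the synopsis, Section 4.1, Schedule of Events footnote 13 and SAP 3.1 on Cohort B patients with SD, since this affects who can complete cycle 4. Which rule is right is not a matter for this review.

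**Cost.** Reasons and dates are already in the eCRF, so no new data are needed. Some reasons need case-by-case classification, because the listed categories do not show whether a patient or investigator decision followed an adverse event. Intervals will be wide, and two related rates will have to be explained side by side.

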4.1 Overview

This is a Phase 2 open-label, study of Lonca-R in previously untreated unfit/frail patients with DLBCL. The study will include a Screening Period (up to 28 days), a Treatment Period (4-6 cycles [each of 3 weeks]), and a Follow-up Period (for up to 5 years after treatment discontinuation) ([Section 4.2](#)).

A response-adapted approach will be used in this study. Two parallel cohorts will enroll patients in the study. Cohort A will enroll unfit patients and Cohort B will enroll frail patients or patients with cardiac comorbidities. Cohort A will assess efficacy and Cohort B will assess the efficacy and tolerability of Lonca-R. Fitness and frailty of the patients will be assessed based on the sGA tool developed by the FIL ([Merli, 2021](#)). See [Section 7.2](#) for details about sGA.

The study will enroll approximately 80 patients (approximately 40 patients in each cohort).

Based on the results from Cohort A and/ or B a protocol amendment will be considered to further evaluate the Lonca-R combination in these patient populations.

Enrolled patients in both cohorts will receive Lonca-R for 3 cycles. Patients who achieve CR after 3 cycles of Lonca-R treatment will continue to receive one additional cycle of Lonca-R. Patients who achieve PR after 3 cycles of Lonca-R will continue to receive additional 3 cycles of Lonca-R. Additionally, for Cohort B only, patients who achieve SD and derive clinical benefit per the treating physician may also continue to receive additional 3 cycles of Lonca-R. Details of dosing regimen are described in [Section 6.3 \(Table 4\)](#), (see [Figure 2](#)).

The duration of the study participation for each patient is defined as the time from the date of signed written informed consent to the completion of the follow-up period, withdrawal of consent, loss to follow-up, or death, whichever occurs first. Each patient enrolled in both cohorts will have the same duration of study participation.

18 weeks) or unacceptable toxicity, or other discontinuation criteria (see [Section 5.5](#)), whichever occurs first. Details of the treatment regimen are described in [Table 4](#).

